#### **Lenalidomide Starting Dose (Cycle 4) Based on Renal Function Prior to Cycle 4 of Treatment**

---

Baseline Calculated Creatinine Clearance (by Cockcroft-Gault)	Starting Lenalidomide Dose
$\geq 60 \text{ ml/min}$	10mg daily on Days 1-28 of each 28-day cycle
$\geq 30 \text{ and } < 60 \text{ ml/min}$	5mg daily on Days 1-28 of each 28-day cycle

At investigator discretion, subjects who have a CrCl between 30-60ml/min may have their lenalidomide dose increased from 5mg to 10mg at the start of cycle 5 or at the start  
Amendment 5 Dated 03/02/2016

---

of subsequent treatment cycles, if they tolerated the prior treatment cycle without requiring dose modifications, interruptions or delays due to toxicity. The maximum allowable target dose for all study subjects is 10 mg daily on Days 1-28 of each 28-day cycle.

Dosing should be at approximately the same time each day but the time of day may be determined per patient to manage any side effects. Only enough lenalidomide for one cycle of therapy will be supplied to the patient each cycle. Prescriptions must be filled within 7 days. If a dose of lenalidomide is missed, it should be taken as soon as possible on the same day. If it is missed for the entire day, it should not be made up. Patients who take more than the prescribed dose of lenalidomide should be instructed to seek emergency medical care if needed and contact study staff immediately.

Subjects experiencing adverse events may need study treatment modifications (See section 5.5).

See Section 5.6.1.1 for allopurinol and oral hydration requirements as prophylaxis against tumor lysis syndrome (TLS).

See Section 5.6.1.2 for prophylactic anti-coagulation.

See Section 5.6.1.5 for concomitant antimicrobial prophylactic therapy

#### **5.5.3.1 Special Handling Instructions**

Females of childbearing potential should not handle or administer lenalidomide unless they are wearing gloves.

#### **5.5.3.2 Record of administration**

Accurate records will be kept in the source documents of all drug administration (including prescribing and dosing).

#### **5.5.3.3 Lenalidomide Dose Continuation, Modification and Interruption**

Sections below describe dose reduction steps, instructions for initiation of a new cycle of therapy and dose modifications during a cycle of therapy.

Amendment 5 Dated 03/02/2016

Additionally, at the discretion of the investigator, lenalidomide may be continued beyond cycle 12 on all patients who have achieved a complete response, partial response or stable disease.

#### **5.5.3.4 Dose Modification Steps**

Lenalidomide dose reductions should be taken one dose level at a time per the table below. Similarly, if lenalidomide dose escalation (or re-escalation) is permitted, it should be done one dose level at a time according to the table below (reverse of the dose reduction steps). See Section 5.5.3.6 for instructions related to lenalidomide dose re-escalation.

**Table 1: Lenalidomide Dose Modification Steps**

Current Lenalidomide Dose	One Level Dose Reduction
10 mg daily on Days 1-28 every 28 days	5 mg daily on Days 1-28 every 28 days
5 mg daily on Days 1-28 every 28 days	5 mg every other day during Days 1-28 every 28 days*
5 mg every other day during Days 1-28 every 28 days*	See * below

\* Lenalidomide 5 mg every other day is the minimum lenalidomide dose. Lenalidomide will be discontinued in patients who cannot tolerate this dose. However, patients who experience toxicity requiring dose reduction while receiving lenalidomide 5 mg every other day may, at the discretion of their physician, have their dose held until toxicity resolves as described in Sections 5.5.3.6, and then restart lenalidomide 5 mg every other day. If the same toxicity recurs at lenalidomide 5 mg every other day, consideration should be given to discontinuing lenalidomide.

**5.5.3.5 Instructions for Initiation of a New Lenalidomide Cycle**

A new course of treatment may begin on the scheduled Day 1 of a new cycle if:

- The ANC is  $\geq 500/\text{mm}^3$ ;
- The platelet count is  $\geq 25,000/\text{mm}^3$ ;
- Any drug-related rash or neuropathy that may have occurred has resolved to  $\leq$  grade 1 severity;
- Tumor lysis syndrome (TLS) has not exceeded grade 1 severity during previous cycle (see Appendix: Cairo-Bishop Definition of Tumor Lysis Syndrome);
- If TLS  $\geq$  grade 2 during previous cycle (see Appendix: Cairo-Bishop Definition of Tumor Lysis Syndrome), electrolyte abnormalities have resolved to  $\leq$  grade 0 severity;
- Any other drug-related adverse events that may have occurred have resolved to  $\leq$  grade 2 severity.

If these conditions are not met on Day 1 of a new lenalidomide cycle, the subject will be evaluated weekly and a new cycle of treatment will not be initiated until the toxicity has resolved as described above.

**5.5.3.6 Instructions for lenalidomide dose modifications or interruption**

Dose delay and dose reduction rules are as follows and in the table below.

- Lenalidomide dose reduction steps are outlined in Section 5.5.3.4
- For treatment interruptions during a cycle, the 28-day schedule of each cycle will continue to be followed. Missed doses of lenalidomide are not made up.
- For treatment interruptions that delay the scheduled start of a new cycle, when toxicity has resolved as required to allow the start of a new cycle (Section 5.5.3.5), the restart day of therapy becomes Day 1 of the next cycle.

---

Dose re-escalation following dose reductions due to neutropenia, thrombocytopenia, tumor lysis syndrome, or tumor flare:

- If the dose of lenalidomide has been reduced for neutropenia or thrombocytopenia, lenalidomide dose re-escalation is permitted if the subject completes one full cycle without experiencing any toxicity that requires dose interruption or reduction.
- If the dose of lenalidomide has been dose reduced for tumor lysis syndrome, lenalidomide dose re-escalation is permitted if the subject completes one full cycle without experiencing a laboratory TLS or  $\geq$  Grade 1 TLS (see Appendix H: Cairo-Bishop Definition of Tumor Lysis Syndrome), unless the subject requires a dose interruption/reduction for other toxicity.
- If the dose of lenalidomide has been dose reduced for tumor flare, lenalidomide dose re-escalation is permitted if the subject completes one full cycle without experiencing  $\geq$  Grade 1 tumor flare, unless the subject requires a dose interruption/reduction for other toxicity.
- If any of the above conditions are met, the lenalidomide dose may be increased by one dose level at the initiation of a new cycle of therapy up to the maximum allowable target dose (see Section 5.5.3 for the maximum allowable target dose and Section 5.5.3.4, Table 1, for appropriate dose escalation steps [reverse of the dose reduction steps in Table 1]
- Serum chemistry and uric acid should be closely monitored for signs of laboratory or clinical TLS (see Appendix H: Cairo-Bishop Definition of Tumor Lysis Syndrome) following lenalidomide dose re-escalation (see Section 2, Schedule of Study Assessments, for details regarding serum chemistry and uric acid monitoring).
- TLS prophylaxis with allopurinol and hydration as described in Section 5.6.1.1 should be considered with each dose re-escalation.

**Table 2: Dose Modifications**

NCI CTC Toxicity Grade	Dose Modification Instructions (also see Instructions for Initiation of a New Cycle above)
Grade 3 neutropenia associated with fever (temperature <math>\geq 38.5^{\circ}\text{C}</math>) or Grade 4 neutropenia	
 
Hold (interrupt) lenalidomide dose. Omitted doses are NOT made up.
 
Follow CBC weekly.
 
First episode: If neutropenia resolves to <math>\leq</math> grade 3 without fever prior to the scheduled end of the current cycle, restart lenalidomide at the current dose level and continue through the scheduled end of the current cycle. Otherwise, omit for remainder of cycle and restart lenalidomide at the current dose level at the start of the next cycle.
 
Second and subsequent episodes: If patient is receiving supportive care with colony-stimulating factors, the dosage will be held until the grade 4 neutropenia resolves. At that time, the current dose level may be maintained at the investigator's discretion.
 
If colony stimulating factors are not being utilized, when neutropenia resolves to <math>\leq</math> grade 3 without fever prior to the scheduled end of the current cycle, restart lenalidomide at the next lower dose level and continue through the scheduled end of the current cycle. Otherwise, omit for remainder of cycle and restart lenalidomide at the next lower dose level at the start of the next cycle.
 

Thrombocytopenia <math>\geq</math>Grade 4 (platelet count <math>< 25,000/\text{mm}^3</math>)	
 
Hold (interrupt) lenalidomide dose. Omitted doses are NOT made up.
 
Follow CBC weekly.
 
If thrombocytopenia resolves to <math>\leq</math> grade 3 prior to the scheduled end of the current cycle, restart lenalidomide at next lower dose level and continue through the scheduled end of the current cycle. Otherwise, omit for remainder of cycle and restart lenalidomide at the next lower dose level at the start of the next cycle.
 

Platelet count <math>< 50,000/\text{mm}^3</math>	
 
Hold prophylactic anti-coagulation, if applicable.
 
Restart prophylactic anti-coagulation when platelet count is <math>\geq 50,000/\text{mm}^3</math>.
 

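### The growth-factor branch of the Table 2 neutropenia row omits the no-fever condition that the row's other two branches set for restarting lenalidomide mid-cycle

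*Combined protocol and SAP*

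**What the plan says.** The neutropenia row of Table 2 (Section 5.5.3.6) has two triggers. One opens with "Grade 3 neutropenia associated with fever (temperature", the threshold being 38.5 °C or above. The other is grade 4 neutropenia, with or without fever. The first instruction in the row is to interrupt lenalidomide. Three branches then say how the interruption ends.

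- **First episode:** restart within the cycle requires neutropenia at or below "grade 3 without fever prior to the scheduled end of the current cycle, restart lenalidomide at the current dose level".
- **Second and later episodes, no growth factor:** restart within the cycle requires neutropenia at or below "grade 3 without fever prior to the scheduled end of the current cycle, restart lenalidomide at the next lower dose level".
- **Second and later episodes, on colony-stimulating factors:** "the dosage will be held until the grade 4 neutropenia resolves", after which "the current dose level may be maintained at the investigator's discretion". Fever is not mentioned.

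Section 5.6.1.6 leaves growth factor to the treating physician, so the third branch can be reached. Section 5.5.3.6 adds that, during an interruption, "the 28-day schedule of each cycle will continue to be followed". If the start of a cycle is delayed, dosing resumes "when toxicity has resolved as required to allow the start of a new cycle", with a reference to Section 5.5.3.5. That section requires an ANC of at least 500/mm³ and includes the general item "Any other drug-related adverse events that may have occurred have resolved to" grade 2 or lower. It does not name fever, and it applies on Day 1 of a new cycle.

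**The concern.** A release rule should not be satisfied while the condition that triggered the hold is still present. Here the third branch looks only at grade 4, although the row is also triggered by febrile grade 3. That has two consequences: one patient state both triggers the hold and ends it, and one kind of episode has no grade 4 neutropenia to resolve.

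What is at stake is dosing safety in patients with recurrent neutropenia. The setting is plausible. Section 3.5 reports myelosuppression as the most common toxicity in one of the cited lenalidomide trials. Section 5.6.1.5 ends antimicrobial prophylaxis at the end of cycle 5, while lenalidomide runs through cycle 12. The discretion granted in the third branch concerns the dose level, so it does not explain why the fever condition is absent. No reason is given elsewhere.

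**Working it through.** There is no plan figure to reproduce. The check compares the wording of the three branches and then looks for a condition elsewhere that would fill the gap.

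**1. States.** Take neutropenia grade 0 to 4, with or without fever: 5 × 2 = 10 states. Treat the end of the hold as permission to resume.

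| State | Row's hold trigger met? | Growth-factor branch: hold ended? | Other two branches: mid-cycle restart allowed? |
|---|---|---|---|
| Grade 4, fever | yes | no | no |
| Grade 4, no fever | yes | no | no |
| **Grade 3, fever** | **yes** | **yes** | no |
| Grade 3, no fever | no | yes | yes |
| Grades 0–2, fever (3 states) | no | yes | no |
| Grades 0–2, no fever (3 states) | no | yes | yes |

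The growth-factor branch ends the hold in 8 states. Exactly one of them, febrile grade 3, also meets the trigger. The other two branches allow restart in 4 states, and none of these meets the trigger. The fever condition is therefore present in 2 of 3 branches, and its absence from the third produces one direct conflict.

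**2. Episode triggered by febrile grade 3.** The third branch covers second and later episodes of either trigger. If the episode never reached grade 4, the stated release event cannot occur. The hold therefore continues. The cycle calendar keeps running and Section 5.5.3.5 decides on Day 1 of the next cycle. What is undefined is at most the rest of one 28-day cycle, and the drug is off during that time.

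**3. Does another section supply the condition?**
- Section 5.5.3.5 governs new cycles, not restart within a cycle, and names no fever condition.
- The Table 2 row for other non-hematologic toxicity starts at grade 3. It is not tied to the 38.5 °C threshold or to neutropenia.
- Section 5.7 relies on general investigator judgment about serious harm.
- Section 5.8 (maintenance) leaves dose reductions to discretion and gives no hold-and-restart rule for neutropenia.

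None gives a mid-cycle condition for fever with grade 3 neutropenia.

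**4. Reach.** The situation needs a second or later episode, growth factor, and fever at grade 3, all together. The documents give no rate for this combination, so no patient count is offered. On timing, 45 patients at 3 or 2 per month take 45/3 = 15 to 45/2 = 22.5 months, consistent with the planned 1.5 years or so. Twelve cycles add 12 × 28 = 336 days, about 11 months, giving 22.5 + 11 = 33.5 months at the slow end. From the protocol date of June 2011 to this March 2016 version is about 56 months. If accrual had started near the protocol date and run to plan (an assumption; actual status is not given), few or no patients would still be in cycles 4–12 under this version.

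**The case against.** The strongest reply is that the row already protects the patient. Its heading covers febrile grade 3 neutropenia and its first instruction is to interrupt the drug, so a patient improving from grade 4 to febrile grade 3 is still inside the row. Unlike the other two branches, the growth-factor branch contains no instruction to restart; it says when the hold ends and permits the dose level to be kept. This stands. A reader might infer that the protocol directs lenalidomide to be given during febrile neutropenia, and the documents do not support that. They contain a release condition that conflicts with the trigger, and a careful physician would probably keep holding.

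A reader might also infer that the other branches bar any restart during fever. They do not. Their fever condition limits restart within the cycle; the fallback of restarting at the next cycle does not repeat it, and Section 5.5.3.5 does not name fever. The contrast between branches is therefore confined to mid-cycle restart.

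Third, the gap for episodes triggered by febrile grade 3 fails in the safe direction, because the drug stays off. That also stands, so this part adds a point about clarity and little about risk.

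Finally, correcting cycles 4–12 now may reach few patients. That depends on accrual, which is not reported. Section 5.5.3.3, which introduces the dose-modification rules, lets lenalidomide continue past cycle 12. Whether Table 2 binds in maintenance is not explicit, but the protocol offers no other rule for interrupting and restarting after neutropenia.

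**Conclusion.** The point holds as a minor error of wording in a safety rule. One of three release branches omits a condition that the other two state for mid-cycle restart. The omission creates one state, febrile grade 3, in which the branch contradicts its own row, and leaves one type of episode without a usable mid-cycle release rule. Confidence is high that the condition is missing. How often it would matter is unknown, and the row heading and investigator judgment make the practical risk small.

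A reader might infer that the trial's results are at risk; they are not. The primary response rate is assessed at the end of cycle 3 (Section 10.1), before lenalidomide starts on Day 1 of cycle 4 (Section 5.5.3). Progression-free and overall survival are reported descriptively, and no planned analysis depends on this rule.

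**What to change.** Reword the growth-factor branch so that it has the same structure as the other two. Suggested text: *For patients on colony-stimulating factors: if, before the current cycle is due to end, neutropenia has come down to grade 3 or lower and there is no fever, resume lenalidomide for the rest of that cycle. If not, give no more in that cycle and resume at the start of the next one under Section 5.5.3.5. In either case the investigator may keep the current dose level.*

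The end-of-cycle limit and the fallback step are both needed. Simply adding a no-fever condition to the present sentence would, read literally, hold growth-factor patients across cycle boundaries for as long as they had fever, which the other branches do not do.

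The cost is one short change in the next amendment. No new tests are needed: the row already asks for weekly blood counts during a hold, and the other branches already require fever status. Some extra doses would be omitted within a cycle and not made up, including in patients at grade 0–2 who are still febrile; the other two branches already accept this. Assuming 3 to 7 extra febrile days at daily dosing (the documents give no figure), and 9 × 28 = 252 planned daily doses in cycles 4–12, that is 3/252 = 1.2% to 7/252 = 2.8% of planned doses for an affected patient. At 5 mg every other day, about half as many doses would be lost.

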**Table 2: Dose Modifications**

NCI CTC Toxicity Grade	Dose Modification Instructions (also see Instructions for Initiation of a New Cycle above)
Laboratory Tumor Lysis Syndrome (TLS) and Grade 1 TLS (see Section 5.6.1.3 and Appendix H: Cairo-Bishop Definition of TLS)	
 
Continue treatment as planned. Maintain current dose.
 
Institute vigorous intravenous hydration and consider rasburicase therapy as needed to reduce hyperuricemia, until correction of electrolyte abnormalities.
 
Other TLS prophylaxis measures outlined in Section 5.6.1.1 should be continued or re-instituted.
 

Tumor Lysis Syndrome (TLS) <math>\geq</math>Grade 2 (see Section 5.6.1.3 and Appendix H: Cairo-Bishop Definition of TLS)	
 
Hold (interrupt) lenalidomide dose. Maintain schedule of cycle. Omitted doses are NOT made up.
 
First episode: If electrolyte abnormalities resolve to Grade 0 prior to the scheduled end of the current cycle, restart lenalidomide at the current dose with appropriate TLS prophylaxis (Section 5.6.1.1) and continue through the scheduled end of the current cycle. Otherwise, omit for remainder of cycle and restart lenalidomide at the current dose at the start of the next cycle with appropriate TLS prophylaxis (Section 5.6.1.1).
 
Subsequent episodes: If electrolyte abnormalities resolve to Grade 0 prior to the scheduled end of the current cycle, restart lenalidomide with appropriate TLS prophylaxis (Section 5.6.1.1) and continue through the scheduled end of the current cycle. Otherwise, omit for remainder of cycle and restart lenalidomide at the start of the next cycle with appropriate TLS prophylaxis (Section 5.6.1.1). At physician discretion, the lenalidomide dose may be restarted at the current dose or lenalidomide may be reduced by 1 dose level.
 
First or subsequent episodes: subjects should be closely monitored for signs of TLS after resuming treatment. To monitor for TLS, serum chemistry and uric acid tests should be performed at least every week following re-initiation of lenalidomide for 4 consecutive weeks and on Day 3 or Day 4 following re-initiation of lenalidomide. See Section 2, Schedule of Study Assessments, for additional specifics regarding serum chemistry and uric acid testing.
 

**Table 2: Dose Modifications**

NCI CTC Toxicity Grade	Dose Modification Instructions (also see Instructions for Initiation of a New Cycle above)
Non-blistering rash  Grade 3	
 
• If Grade 3, hold (interrupt) lenalidomide dose. Follow weekly.
 
• If the toxicity resolves to <math>\leq</math> grade 1 prior to the scheduled end of the current cycle, restart lenalidomide at next lower dose level and continue through the scheduled end of the current cycle. Otherwise, omit for remainder of cycle and reduce the dose of lenalidomide by 1 dose level at the start of the next cycle. Omitted doses are not made up.
 

	
 
• If Grade 4, discontinue lenalidomide. Remove patient from study.
 

Desquamating (blistering) rash- any Grade	
 
• Discontinue lenalidomide. Remove patient from study.
 

	
 
• If Grade 3, hold (interrupt) lenalidomide dose. Follow at least weekly.
 
• If the toxicity resolves to <math>\leq</math> grade 1 prior to the scheduled end of the current cycle, restart lenalidomide at next lower dose level and continue through the scheduled end of the current cycle. Otherwise, omit for remainder of cycle and reduce the dose of lenalidomide by 1 dose level at the start of the next cycle. Omitted doses are not made up.
 

Neuropathy  Grade 3	
 
• If Grade 3, hold (interrupt) lenalidomide dose. Follow at least weekly.
 
• If the toxicity resolves to <math>\leq</math> grade 1 prior to the scheduled end of the current cycle, restart lenalidomide at next lower dose level and continue through the scheduled end of the current cycle. Otherwise, omit for remainder of cycle and reduce the dose of lenalidomide by 1 dose level at the start of the next cycle. Omitted doses are not made up.
 

	
 
• If Grade 4, discontinue lenalidomide. Remove patient from study.
 

Venous thrombosis/embolism <math>\geq</math> Grade 3	
 
• Hold (interrupt) lenalidomide and start therapeutic anticoagulation, if appropriate.
 
• Restart lenalidomide at investigator's discretion (maintain dose level).
 
• See Anticoagulation Consideration (Section 5.6.1.2).
 

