 Cycle 4 may begin up to 14 days after cycle 3 bone marrow biopsy to allow for results of response assessments to be available.

 CBC and CMP only every 4 weeks. See Section 5.8. Any grade 3 or 4 cytopenia will be recorded as an adverse event during Maintenance Therapy. No other adverse events will be recorded during Maintenance Therapy

 Upon discontinuation of study therapy, any diagnostic testing will be at the discretion of the physician.

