##### **5.5.2.1.1 Liver Chemistry Stopping Criteria:**

1. ALT > 3xULN and bilirubin  $\geq$  2xULN (>35% direct bilirubin; bilirubin fractionation required)\*
2. ALT > 8xULN
3. ALT  $\geq$  5xULN for more than 2 weeks

\*NOTE: serum bilirubin fractionation should be performed if testing is available. If testing is unavailable and a subject meets the criterion of total bilirubin  $>2.0 \times$  ULN, then the following actions must still be performed.

When any of the liver chemistry stopping criteria is met, do the following:

- Immediately withdraw investigational product
- Report the event to NOVARTIS and Celgene Corporation within 24 hours of learning its occurrence
- All events of ALT  $\geq$  3xULN and bilirubin  $\geq$  2xULN (>35% direct bilirubin), termed 'Hy's Law', must be reported as an SAE.

NOTE: serum bilirubin fractionation should be performed if testing is available. If testing is unavailable, record presence of detectable urinary bilirubin on dipstick, indicating direct bilirubin elevations and suggesting liver injury.

---

- Perform liver event follow up assessments, and monitor the subject until liver chemistries resolve, stabilize, or return to baseline values as described below.
- Withdraw the subject from the study (unless further safety follow up is required) after completion of the liver chemistry monitoring as described below.
- Do not re-challenge with investigational product.

In addition, for criterion 1:

- Make every reasonable attempt to have subjects return to clinic within 24 hours for repeat liver chemistries, liver event follow up assessments (see below), and close monitoring
- A specialist or hepatology consultation is recommended
- Monitor subjects twice weekly until liver chemistries (ALT, AST, alkaline phosphatase, bilirubin) resolve, stabilize or return to within baseline values

For criteria 2 and 3:

- Make every reasonable attempt to have subjects return to clinic within 24-72 hrs for repeat liver chemistries and liver event follow up assessments (see below)
- Monitor subjects weekly until liver chemistries (ALT, AST, alkaline phosphatase, bilirubin) resolve, stabilize or return to within baseline values; criterion 5 subjects should be monitored as frequently as possible.

Subjects with ALT  $\geq 5$ xULN which exhibit a decrease to ALT  $\geq 3$ xULN, but  $< 5$ xULN and bilirubin  $< 2$ xULN without hepatitis symptoms or rash, and who can be monitored weekly for 4 weeks:

- Can continue ofatumumab

---

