### **5.9 Follow-Up**

If a subject discontinues study treatment at any time during cycles 1-12, “Discontinuation from Protocol Therapy” on the Schedule of Assessments, Section 2 will be performed. If the bone marrow biopsy and CT scans have been performed in the past 28 days to determine progression of disease, it is not necessary to repeat them.

The subject will then enter the follow-up period unless consent is withdrawn. If a subject enters Maintenance Therapy (MT) after cycle 12, the follow-up period will begin after discontinuation of lenalidomide in MT. If a subject completes 12 cycles and does not enter MT, follow-up will begin at the completion of cycle 12.

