#### **6.2.4 Time Period and Frequency of Detecting and SAEs**

Once an investigator determines that an event meets the protocol definition of an SAE, the SAE will be reported to Novartis within 24 hours of being notified of the event. All SAEs regardless of relationship to investigational product will be collected from the first dose of investigational product to after the last dose of investigational product (minimum of 6 months or until the end of the follow-up period which ever is longer). All SAEs regardless of causality will be collected until the end of the follow-up period.

Amendment 5 Dated 03/02/2016

---

From the time a subject consents to participate in and completes the study all SAEs assessed as related to study participation (e.g., protocol-mandated procedures, invasive tests, or change in existing therapy) or related to NOVARTIS concomitant medication, will be reported promptly to NOVARTIS.

Any SAE brought to the investigator's attention after the subject has completed the study and considered by the investigator as possibly related to investigational product must be reported to NOVARTIS.

This includes serious, related, not related, labeled (expected) and, unlabeled (unexpected) adverse experiences. All deaths during treatment or within 30 days following completion of active protocol therapy must be reported within 24 hours.

Any SAEs experienced after the follow-up period should only be reported to Novartis if the investigator suspects a causal relationship to the study drug. Recurrent episodes, complications, or progression of the initial SAE must be reported as follow-up to the original episode within 24 hours of the investigator receiving the follow-up information. A SAE occurring at a different time interval or otherwise considered completely unrelated to a previously reported one should be reported separately as a new event. The end date of the first event must be provided.

The original copy of the SAE Report and the fax confirmation sheet must be kept within the Trial Master File at the study site.

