#### **10.6 Evaluation of Response**

All patients treated on the study must be assessed for response to treatment, even if there are major protocol treatment deviations or if they are ineligible. Each patient will be assigned one of the following categories: 1) complete response, 2) partial response, 3) stable disease, 4) progressive disease, 5) early death from malignant disease, 6) early death from toxicity, 7) early death because of other cause, or 9) unknown (not assessable, insufficient data). [Note: By arbitrary convention, category 9 usually designates the “unknown” status of any type of data in a clinical database.]

Patients in response categories 4-9 should be considered as failing to respond to treatment (disease progression). Thus, an incorrect treatment schedule or drug administration does not result in exclusion from the analysis of the response rate.

---

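### Toxicity rules that take patients off the study contradict the follow-up and SAE sections, so PFS, OS and late SAE data can be lost for treatment-related reasons; footnote 15 separately contradicts 5.4 and 5.9 on discontinuation testing

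*Combined protocol and SAP*

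**What the plan says.** **Rules that end study participation.** Table 2 (5.5.3.6) says "If Grade 4, discontinue lenalidomide. Remove patient from study" for grade 4 non-blistering rash and grade 4 neuropathy, and gives the same pair of instructions for desquamating rash of any grade. For the liver criteria, 5.5.2.1.1 first withdraws the investigational product and later adds: "Withdraw the subject from the study (unless further safety follow up is required) after completion of the liver chemistry monitoring as described below". Section 5.1 also takes patients with progression off the study.

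**Rules that keep patients in follow-up.** Section 5.9 covers any stop during cycles 1-12. It says that the discontinuation column "on the Schedule of Assessments, Section 2 will be performed", waives marrow and CT only if they were done in the past 28 days to determine progression, and continues: "The subject will then enter the follow-up period unless consent is withdrawn". Section 5.4 likewise calls for off-study evaluations. Section 6.2.4 states: "All SAEs regardless of causality will be collected until the end of the follow-up period", with a minimum of 6 months.

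**Testing at discontinuation.** Footnote 15 of the Schedule of Study Assessments, attached to the discontinuation column, says: "Upon discontinuation of study therapy, any diagnostic testing will be at the discretion of the physician".

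**Analysis.** Section 10.4 includes every patient who receives at least one dose. Those who leave before their response evaluation count as non-responders, and their time-to-event data are censored at last assessment. PFS and OS are descriptive. Section 10.6 adds: "All patients treated on the study must be assessed for response to treatment, even if there are major protocol treatment deviations".

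**The concern.** The documents never define removal from the study. If staff take Table 2 or 5.5.2.1.1 at their word, follow-up ends because of a drug toxicity. If they take 5.9 at its word, it continues. Both sets of instructions are in force.

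Two things are at stake. First, a patient removed for toxicity has stopped therapy, so the later risk of progression or death may differ from that of patients who stay. Kaplan-Meier estimation assumes that it does not. Second, SAEs arising after removal may not be sought, although 6.2.4 wants them.

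Footnote 15 is a separate contradiction. PFS is the more exposed endpoint here. The 6-monthly follow-up in 5.4 is written only for subjects who completed 12 cycles, and outside the listed time points footnotes 3 and 4 leave marrow and CT to the physician. For an early stopper, the discontinuation tests may therefore be the last disease assessment that the protocol asks for.

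**Working it through.** **1. Does removal mean only stopping drug?** The text does not settle it.
- In 5.5.2.1.1, withdrawing the product and withdrawing the subject are separate steps. The second follows liver monitoring and carries its own exception for further safety follow-up.
- Table 2 also gives two instructions, stop the drug and then remove from study. The footnote to the dose-modification steps in 5.5.3.4 speaks only of discontinuing lenalidomide.
- Against that, 5.1 uses removal for progression, yet OS is an endpoint and the schedule has a survival follow-up row. This suggests that the authors may have meant off therapy.

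**2. Where the sections disagree.**

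| Question | One instruction | The other |
|---|---|---|
| Follow-up after a toxicity stop | Ends: Table 2, 5.5.2.1.1 (liver, with exception) | Continues unless consent is withdrawn: 5.9 |
| SAE collection | Ends with participation, if removal is read literally | To end of follow-up, at least 6 months: 6.2.4 |
| Testing at discontinuation | Discretionary: footnote 15 | Performed: 5.4, 5.9 (CT and marrow waived if done in past 28 days) |

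**3. Primary endpoint.** The design in 10.1 reproduces. With 26 then 19 patients and cut-offs of 15 and 32:
- early stopping = P(X1 ≤ 15 | 26, p) = 0.479 at p = 0.60 and 0.008 at p = 0.80 (stated 0.48 and 0.01);
- success = Σ over x1 = 16 to 26 of P(X1 = x1) × P(X2 ≥ 33 − x1 | 19, p) = 0.0445 at 0.60 and 0.900 at 0.80 (stated 0.045 and 0.90).

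Lenalidomide starts in cycle 4 and the primary response is taken at the end of cycle 3, so the Table 2 removals leave these figures alone. A liver withdrawal before that assessment counts as a non-response under 10.4.

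**4. PFS.** The 10.4 censoring sentence is written for patients lost before their response evaluation. It is the only censoring rule given, so I take it to cover later removals too. No removal rate is stated, so everything below is assumed. Each patient is 1/45 = 2.2% of the trial.

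*Moderate case:* 5-15% removed early (about 2 to 7 of 45), with 24-month PFS of 40% in them and 60% in the rest.
- True PFS at 5% removed: 0.95 × 0.60 + 0.05 × 0.40 = 0.59.
- True PFS at 15% removed: 0.85 × 0.60 + 0.15 × 0.40 = 0.57.
- Kaplan-Meier with the removed group censored early: about 0.60, so too high by 1 to 3 points.

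*Harsh case:* k patients are censored at removal and all have the event before the landmark, while the rest have PFS S. The overstatement is S − S(45 − k)/45 = S × k/45.
- At S = 0.80: 1.8 points (k = 1), 3.6 (k = 2), 5.3 (k = 3), 8.9 (k = 5).
- At k = 5, with S from 0.70 to 0.90: 7.8 to 10.0 points.

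*Scale:* with 45 patients and PFS of 60%, ignoring other censoring, the standard error is √(0.60 × 0.40/45) = 7.3 points and the 95% half-width is 1.96 × 7.3 = 14.3 points.

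**The case against.** The best defence is that 5.9 already governs. It applies to any stop in cycles 1-12, its only exception is withdrawn consent, and Table 2 is a dose-modification table whose wording may just mean off protocol therapy. That reading is reasonable, and it is why loss of data is a risk here and not an established fact. It does not remove the contradiction, because the liver section separates stopping drug from leaving the study.

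Several stronger inferences are tempting, and the documents do not support them.
- *SAE data are lost completely after removal.* Section 6.2.4 has no toxicity exception, sets a 6-month minimum, and asks for possibly related SAEs even after study completion. Footnote 9 adds a safety assessment 28 days after the last dose. Section 6.2.2 records every liver-stopping event as an SAE. Footnote 15 concerns diagnostic testing, not SAE or survival reporting.
- *Data are lost selectively in the patients with the worst toxicity.* Footnote 15 covers every discontinuation. Table 2 keeps patients with grade 4 neutropenia, grade 4 thrombocytopenia, tumor lysis syndrome of grade 2 or more and thrombosis of grade 3 or more on study, while desquamating rash triggers removal even when mild.
- *The primary result is compromised.* The Table 2 rules act too late for that. For an early liver withdrawal without an assessment, non-response is a prespecified and conservative outcome, and 10.6 has an unknown category that counts as failure.

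It is also fair that the moderate-case bias is small beside the sampling error and that PFS and OS drive no decision.

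**Conclusion.** The contradiction stands. Table 2 and 5.5.2.1.1 end study participation for certain toxicities, while 5.9 and 6.2.4 continue follow-up and SAE collection for the same patients. Footnote 15 conflicts with 5.4 and 5.9 on whether discontinuation testing is required.

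If the removal rules are followed literally, the descriptive PFS and OS estimates can be biased and late SAEs can be missed. The size cannot be known from the documents. It is about 1 to 3 points of 24-month PFS under the moderate assumptions and up to 10 points in the harshest case shown. The bias is upward only if removed patients do worse than those who stay, and no OS effect has been calculated. The primary endpoint, alpha and power are not changed by the Table 2 rules.

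A reader might infer that these data will certainly be lost. The documents support only that conflicting instructions make the loss possible. The point is worth correcting because the text is contradictory and the repair is cheap, not because the main conclusion is at risk.

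**What to change.** Leave every treatment-stopping rule as it is and separate it from study participation.

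1. In Table 2 and 5.5.2.1.1, replace removal or withdrawal from the study with removal from protocol therapy, with follow-up for progression, survival and SAEs continuing per 5.9 and 6.2.4 unless consent is withdrawn.
2. Use the same wording in 5.1 for patients removed for progression, so that survival follow-up continues.
3. Reconcile footnote 15 with 5.4 and 5.9. The documents do not show which was intended, so the study team should decide. This point does not itself call for a mandatory marrow or CT.

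One limit remains. Section 5.9 sets no disease-assessment schedule for early stoppers, so the change protects survival and SAE data more fully than PFS. The follow-up text should say how progression will be ascertained in these patients.

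The cost is wording in four places and a few more follow-up contacts, which 5.9 already calls for. Sample size and decision rules do not change.
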